reduction in the risk of dementia in elderly patients with type 2 diabetes [15][16], but these studies are all diabetes patients in a large database. Comparing the use of metformin to reach the conclusion is subject to more interference factors. Other early studies have shown that long-term use of metformin even increases the risk of dementia [17], which may be related to vitamin B12 deficiency, the duration of metformin use, and the course of diabetes. Short-term controlled studies with small samples have shown that metformin can penetrate the blood-brain barrier and improve learning, memory and attention in non-diabetic MCI patients [18].

In summary, as a widely used traditional hypoglycemic drug, metformin has been shown to improve central insulin resistance in basic studies and has been proved to be feasible in clinical studies of diabetic patients. However, there are few studies investigating the efficacy of metformin in improving cognitive function in elderly obese patients with MCI.

七、 Research method

1. overall design

This study was a prospective, randomized controlled, single-center clinical cohort study. Those subjects who met the inclusion criteria were included in the study after they signed the informed consent. The study was conducted in the Drug Clinical Laboratory of Endocrinology Department, Huadong Hospital. The subjects were randomly divided into two groups using random number method. In the first group, subjects received metformin sustained-release tablets (1500mg once a day or reduced to the maximum tolerated dose if intolerable) and lifestyle intervention guidance. Subjects in the second group received only lifestyle intervention guidance. All subjects were followed up for 26 weeks with a diary card for dosing and adverse events and a telephone visit every 4 weeks 3 days after randomization.

2. Study Population

Any elderly subject who is overweight or obesity with mild cognitive impairment and is admitted to the study center may be considered for this study. The primary investigator bore the primary responsibility for subject enrollment. You can expect to limit the speed of grouping for the following reasons:

- The number of outpatient visits and the number of subjects who met the inclusion and exclusion criteria;
- The willingness and informed consent of the subjects were evaluated at baseline.

八、 Inclusion criteria, exclusion criteria and exit criteria of subjects

1. Inclusion criteria

- A. age: 60 -75 years;

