- B. Body mass index: $\geq 24\text{kg}/\text{m}^2$;
- C. glycated hemoglobin $< 8.5\%$;
- D. The scores of the MoCA scale are 20–26 (education > 10 years) or 20–25 (education ≤ 10 years);
- E. sign informed consent forms;

2. Exclusion criteria

- A. Anyone who takes any hypoglycemic drug within 8 weeks prior to enrollment;
- B. type 1 diabetes;
- C. Central nervous system magnetic resonance imaging cannot be completed;
- D. A history of alcohol or drug addiction;
- E. Severe gastrointestinal diseases, history of gastrointestinal surgery, severe cardiopulmonary dysfunction, malignant tumor and other diseases;
- F. Abnormal liver function (liver enzyme index is more than 2.5 times the upper limit of the reference range) or renal function (estimated glomerular filtration rate $< 45\text{ mL/min}$);
- G. There were relevant situations that the investigator judged were not suitable for inclusion in the study.

3. Exit criteria

All subjects had the right to withdraw from the study at any stage of the study and the investigator had the right to discontinue observation of subjects who:

- 1) Continuing to participate in the seminar would cause unnecessary damages to the subjects;
- 2) The subjects had poor compliance and did not cooperate with the researchers in

relevant examinations and interventions;

- 3) Subjects who were found not to meet the inclusion criteria after participating in the study;
- 4) Subjects who were found to meet the exclusion criteria after participation in the study.

九、 Sample size assessment

The change in blood flow volume of cerebral regions shown by fMRI after nasal insulin inhalation was used as the research endpoint. According to the results of previous literature, the difference between groups after drug intervention was 20%, and the standard deviation was 20%. When the accuracy was 0.05 and the test efficiency $1-\beta$ was 0.8, the required sample size for each group was obtained from the sample size calculation formula: $n_1=n_2=23$. Considering the existence of a certain shedding ratio, and calculated based on the shedding rate of 15%, 54 patients, 27 in each group, were to be included in the study.

十、 Study Endpoints

1. Effectiveness

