The main evaluation indexes were the changes of cerebral blood flow shown by fMRI after nasal insulin inhalation. The secondary evaluation index was MoCA scale score. To explore the influence of metformin intervention on cognitive dysfunction under different glycosylated hemoglobin baselines.

2. Safety

Intestinal reaction, such as abdominal pain, diarrhea, abdominal distension; other uncomfortable symptoms or events affecting living activities.

十一、 Research process

1. **Screening period:** whether the screening met the inclusion criteria, and there was no exclusion criterion.
2. **V0:** A total of 54 elderly subjects who were expected to be enrolled as overweight or obesity with MCI, taking medical history (previous illness, medication history and concomitant medication, smoking history, alcohol consumption history, and educational level), demographic data (gender, date of birth), comprehensive physical examination (height, weight, body temperature, heart rate, respiration, blood pressure, waist circumference, hip circumference, body composition, nervous system, and cardiopulmonary abdomen), Laboratory tests (fasting blood glucose, fasting insulin, fasting C-peptide, glycated hemoglobin, blood lipids, routine blood tests, liver and kidney function, and routine 12-lead electrocardiogram), MoCA scale evaluation, and nasal insulin inhalation combined with fMRI imaging were performed.
54 patients were randomly divided into two groups. In the first group, subjects received metformin sustained-release tablets (1500mg once a day or reduced to the maximum tolerated dose if intolerable) and lifestyle intervention. Subjects in the second group received only lifestyle intervention guidance. All subjects were followed for a 26-week follow-up period and diary cards were issued to record dosing and adverse events. A 24-hour meal was recorded during the first week of intervention; Exercise instruction.
3. **V1** (intervention 4 weeks): The patient was interviewed by phone for any adverse events.
4. **V2** (eight weeks of intervention): The patient was interviewed by phone for any adverse events.
5. **V3** (intervention 12 weeks): The patient was interviewed by phone for any adverse events.
6. **V4** (intervention for 16 weeks): The patient was interviewed by phone for any adverse events.

7. **V5** (intervention of 20 weeks): The patient was interviewed by phone for any adverse events.

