8. **V6** (24 weeks of intervention): The patient was interviewed by phone for any adverse events.

9. **V7** (intervention for 26 weeks): Medical history (previous disease history, medication history and concomitant medication history, smoking history, drinking history, and educational level) demographic data (gender, date of birth), comprehensive physical examination (height, weight, temperature, heart rate, respiration, blood pressure, waist circumference, hip circumference, body composition, nervous system, and cardiopulmonary abdomen), laboratory tests (fasting blood glucose, fasting insulin, fasting C-peptide, glycated hemoglobin, blood lipid, blood routine, liver and kidney function, routine 12-lead electrocardiogram), MoCA scale evaluation, and nasal insulin inhalation combined with fMRI imaging were collected again.

10. **V8**: A safety visit 4 weeks after the end of the intervention to ask the patient over the phone for any adverse events. The report was analyzed and recommendations were made for treatment protocol adjustments based on the report.

[figure not shown]

Figure 1 research flow chart

visit	V-1	VO	V1	V2	V3	V4	V5	V6	V7	V8
stage	screening period	baseline visit	telephone follow-up	follow-up at the end of the treatment period	follow-up after the treatment period					
time(weeks)	2	0	4	8	12	16	20	24	26	30
window period (days)			±3d	±3d	±3d	±3d	±3d	±3d		±7d
sign the informed consent form	√									
check the inclusion and exclusion criteria	√	√								
formulate or adjust the medication plan for lowering blood glucose		√								
collect medical history (previous illness, medication history and concomitant medication, smoking history, alcohol consumption history, and educational level)			√						√	
demographic data (gender, date of birth)			√						√	
comprehensive physical examination (height, weight, body temperature, heart rate, respiration, blood pressure, waist circumference, hip circumference, nervous system, and cardiopulmonary abdomen)			√						√	
body composition			√						√	
routine 12-lead electrocardiogram		√							√	
routine blood tests		√							√	
liver and kidney function, eGFR(based on renal function assessment)			√						√	
blood lipids(CHO, TG, HDL-C, and LDL-C)			√						√	
fasting blood glucose, fasting insulin, fasting C-peptide			√						√	
HbA1c			√						√	
MoCA scale evaluation			√						√	
nasal insulin inhalation combined with fMRI imaging			√						√	
diet and exercise guidance		√								

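### The exit criteria allow observation itself to be ended by an investigator who can know the arm, and no week-26 fMRI or MoCA is sought afterwards

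*Protocol*

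**What the plan says.** Section 八, 3 of the protocol first gives subjects the right to withdraw, then adds that "the investigator had the right to discontinue observation of subjects who" fall under one of four criteria. Two of these involve judgement during follow-up. Criterion 1 reads "Continuing to participate in the seminar would cause unnecessary damages to the subjects". Criterion 2 begins "The subjects had poor compliance and did not cooperate with the researchers" and refers to examinations and interventions. Criteria 3 and 4 concern subjects found after entry to be ineligible.

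Other places bear on the point:

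- **Follow-up.** Section 七, 1 says "All subjects were followed up for 26 weeks with a diary card". Section 十一, V0, says "All subjects were followed for a 26-week follow-up period". Neither says whether this still applies after an exit.
- **Arms.** Metformin plus lifestyle guidance is compared with lifestyle guidance alone. For intolerance the dose is "reduced to the maximum tolerated dose if intolerable".
- **Outcome visits.** V1 to V6 are telephone calls about adverse events. At V7 (week 26), "MoCA scale evaluation, and nasal insulin inhalation combined with fMRI imaging were collected again". The Appendix likewise places MoCA at V0 and V7 only.
- **Early-withdrawal visit.** Note (4) under the follow-up plan asks participants who withdrew early to return fasting within 7 days of the investigator being informed. It does not list fMRI or MoCA.

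**The concern.** Stopping a treatment and stopping data collection are different events, and the exit section provides only for the second. In an open comparison where one arm takes tablets and the other does not, the grounds for exit need not arise equally. Section 十二 expects gastrointestinal reactions because metformin is used, so criterion 1 can be met for that reason in one arm only. Criterion 2 can also differ by arm, though less, because both arms have lifestyle guidance, diary cards and the same examinations. Criteria 3 and 4 rest on eligibility, already checked at screening and baseline, and no difference between arms is expected from them.

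The primary endpoint (fMRI blood flow after nasal insulin) and the secondary endpoint (MoCA) each have a single scheduled post-baseline value. If observation ends before V7, no scheduled interim value can stand in for it. An analysis plan can choose how to handle a missing scan, but it cannot supply the scan.

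**Working it through.** **Planned figures.** Section 九 gives a difference of 20 points, SD 20 points, alpha 0.05, power 0.80, 23 per group, and 27 per group (54 in total) after an allowance for 15% loss. The last step follows from 23 × 1.15 = 26.45, rounded up to 27. The 23 does not follow from the stated inputs: a two-sided test needs 16 per group by the normal approximation and 17 by the t-test. That is a separate matter. Here it means only that 27 per group leaves power to spare (95.0% for a 20-point difference with no losses).

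**Model (assumed, not from the protocol).** Let *b* be the losses per arm for reasons unrelated to outcome, *x* the extra metformin-arm exits due to this clause, and *g* the difference in SD units between the means of retained and removed subjects. The metformin arm without those exits has 27 − *b* subjects, of whom *x* lie *g* below the retained mean. Hence

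bias = *g* × *x* / (27 − *b*) SD, times 20 for points.

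Type I error is the two-sided rejection rate of the t-test with groups of 27 − *b* − *x* and 27 − *b* when the true difference is zero, from the noncentral t distribution with

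noncentrality = bias in SD / √(1/(27 − *b* − *x*) + 1/(27 − *b*)).

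**One case in full** (*b* = 0, *x* = 2, *g* = 1): bias = 2/27 = 0.074 SD = 1.48 points. The standard error is 20 × √(1/25 + 1/27) = 5.55 points. Noncentrality = 1.48/5.55 = 0.267, and type I error = 0.0579.

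**Results.** Each cell gives *g* = 0.5 / *g* = 1.0. The power column takes a true 20-point effect with the bias working against it.

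| *b* | *x* | Groups | Bias, points | Type I error | Power if masked |
|---|---|---|---|---|---|
| 0 | 1 | 26 v 27 | 0.37 / 0.74 | 0.0505 / 0.0520 | 0.939 / 0.930 |
| 0 | 2 | 25 v 27 | 0.74 / 1.48 | 0.0520 / 0.0579 | 0.925 / 0.905 |
| 3 | 1 | 23 v 24 | 0.42 / 0.83 | 0.0506 / 0.0522 | 0.907 / 0.895 |
| 3 | 2 | 22 v 24 | 0.83 / 1.67 | 0.0522 / 0.0588 | 0.888 / 0.859 |

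With no extra exits, power is 0.950 (*b* = 0) or 0.924 (*b* = 3). At *g* = 0 the bias is zero and type I error is 5.0%. A simulation of 200,000 runs at *g* = 1 agrees: 0.0524 and 0.0575 for *b* = 0, and 0.0528 and 0.0588 for *b* = 3.

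**Upper bounds, not expected cases.** Four exits in the metformin arm and none in control (15% of 27 is about 4) give a bias of 1.5 / 3.0 points and type I error of 0.0575 / 0.0805. Eight against none gives 3.0 / 5.9 points and 0.077 / 0.162. Both charge all planned loss, including voluntary withdrawal, to one arm and to this clause. The first does so for one arm's share of the loss, the second for the whole trial's.

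**The case against.** The best case against is that little is at stake and that the clause is read too literally.

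- **Permissive wording in a rough translation.** The right need not be used, the English is loose throughout, and two sections say all subjects are followed for 26 weeks. This is fair, but nothing says that the follow-up statement survives an exit, and the exit section is the specific rule. At the least, the sections must be reconciled.
- **Few subjects are affected.** Intolerance leads first to dose reduction. Criterion 2 joins its two conditions with *and*, so someone who stops tablets but still attends does not clearly meet it, and many who do meet it would miss V7 under any wording. This stands and is why the expected bias is small. It leaves mainly criterion 1.
- **Note (4) may already capture outcomes.** Its waiver of recently repeated examinations implies that some items are repeated, and V7 is the only scheduled on-site visit after baseline, so fMRI and MoCA could be included. That is a possible reading. The visit is still not at week 26, its content is not stated, and it speaks of participants who withdrew, so it may not cover exits decided by the investigator.
- **The gap between removed and retained subjects is assumed.** This is correct: the documents give no basis for it and no exit rates by arm.

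**Conclusion.** The concern holds and should be acted on, at low to moderate weight. As written, the protocol lets someone who can know the allocation end observation of a randomised subject, and it asks for no week-26 outcome from that subject afterwards.

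The expected distortion is small. With one or two extra metformin-arm exits and a gap of 0.5 to 1.0 SD, the bias is 0.4 to 1.7 points (about 2% to 8% of the 20-point target) and type I error is at most 5.88%. If the bias masks a true effect, power is still at least 85.9%, above the planned 80%. These figures rest wholly on the assumed number of exits and the assumed gap, and the direction of bias is unknown. The reason to change the text is that the lost values cannot be recovered and keeping them costs little.

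**What to change.** Reword section 八, 3, for all four criteria, so that a decision about study drug does not end observation. For example: *Every randomised subject is invited to the V7 fMRI and MoCA at week 26 unless consent is withdrawn or the assessment is unsafe.* Reconcile this with the 26-week statements in sections 七, 1 and 十一, and state in Note (4) which examinations the early-withdrawal visit includes and whether it covers exits decided by the investigator. None of this alters any dose or any rule for stopping treatment.

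The cost is protocol wording and some retention effort, using a visit that is already planned. Keeping subjects who have stopped metformin may dilute the estimated effect, and those who refuse examinations will still be missing.

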Title: attending physician

Address: [name]
Shanghai postal code: 200040

[contact]

mobile [contact]

email [contact]

一、 Programme summary

Protocol name	The efficacy and safety of metformin intervention in elderly overweight or obesity with mild cognitive impairment
Version number/ Version date	V1.0 7 August, 2025
Research objects	Elderly overweight or obesity patients with mild cognitive impairment
Research purposes	To explore the efficacy and safety of metformin in sufficient amount in elderly overweight or obese patients with MCI. To provide reliable evidence for the elderly overweight or obese patients with MCI to delay and reverse the cognitive dysfunction.
Research design	This study was a prospective, randomized controlled, single-center clinical cohort study. Elderly subjects who were overweight or obese with MCI and met the inclusion criteria and did not meet the exclusion criteria were included in this study with informed consent. The subjects were randomly divided into two groups using random number method. In the first group, subjects received metformin sustained-release tablets (1500mg once a day or reduced to the maximum tolerated dose if intolerable) and lifestyle intervention guidance. Subjects in the second group received only lifestyle intervention guidance. All subjects were followed for a period of 26 weeks. History collection, body measurement index evaluation, glycolipid metabolism biochemical test, medication record, and MoCA scale evaluation were conducted during the enrollment phase and the end of follow-up. The insulin sensitivity in central nervous system of subjects in the two groups before and after treatment was evaluated by nasal insulin inhalation combined with fMRI.
Inclusion/ exclusion	Inclusion criteria

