At present, the mechanisms of cognitive dysfunction in elderly obese patients include the pathophysiological role of microvascular mechanisms and fat-derived factors [3]. Insulin not only regulates peripheral metabolism, but also acts on the central nervous system to regulate cognitive function. All cell types in the brain have insulin signaling pathways, and some studies have shown that insulin resistance in the brain can damage the plasticity and memory function of hippocampal synapses, leading to cognitive decline [7]. The Montreal Cognitive Assessment Scale (MoCA) is usually used for the evaluation of cognitive function, which includes multiple dimensions such as memory, attention, executive function and language function, with a full score of 30. The score considering the diagnosis of MCI is 20-26 (education > 10 years) or 20-25 (education \leq 10 years) [8]. However, in actual work, scale collection is affected by many factors. fMRI can display the changes of local cerebral blood flow and metabolic activities before the changes of brain structure, so as to understand the changes of brain function in depth. It is an important means for early diagnosis of cognitive dysfunction, efficacy monitoring and mechanism research [9]. The degree of central insulin resistance was assessed by fMRI combined with nasal insulin inhalation to observe the response of different brain regions to insulin. The absence of neuroimaging or neurophysiological reactions after nasal insulin inhalation is suggestive of central nervous system insulin resistance [7]. Previous studies have shown that improving central insulin resistance can delay or even reverse cognitive decline [10]. Therefore, the central insulin resistance observed by fMRI can be used as an objective basis for the assessment of cognitive function.

3. Metformin may improve cognitive dysfunction by improving central insulin resistance in elderly obese patients.

Metformin is widely used as the first-line medication for type 2 diabetes. Basic research showed that metformin had the potential to activate the 5'AMP-activated protein kinase (AMPK) pathway, which played a vital role in the pathogenesis of dementia [11]. Metformin can improve insulin resistance [12], reduce neuronal apoptosis [13], and reduce cerebral oxidative stress and inflammatory response [14]. Recent studies have shown that the use of metformin is associated with a significant

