at any dose or at any time during observation. Adverse events are classified as serious adverse events if one or more of the following criteria are met: 1. Death 2. Life-threatening (meaning that the patient in whom the event occurred was at risk of dying immediately at the time of the event; Does not include those events which, if more serious, could result in the death of the patient) 3. Lead to hospitalization or prolonged hospitalization 4. Lead to permanent or significant loss of labor or disability 5. Congenital malformations. Medical events that have not yet resulted in death, life risk, or hospitalization that, after appropriate medical judgment, may be hazardous to the patient or subject or require medical or surgical treatment to avoid such occurrences should also be considered SAE.

If any adverse event occurs, the patient should report it to the researcher in time. The researcher should make a detailed record at the corresponding position on the case report form. The researcher should assist the patient to actively handle the adverse event and strive for the best prognosis while respecting the patient's will and choice. Meanwhile, possible adverse events are prevented and treated. As metformin was used in this study, it was expected that possible adverse events in this study would include: gastrointestinal reaction conditions, such as abdominal pain, diarrhea, and abdominal distension. In the case of serious adverse events, the Ethics Committee and relevant health authorities will be reported within 24 hours and the subject will be treated promptly.

十三、 Statistical Analysis Plan

SPSS 22.0 statistical analysis software was used for calculation. All statistical tests were performed using a two-sided test, and $P \leq 0.05$ was considered statistically significant for the difference tested. Enumeration data were described by constituent ratio, and measurement data were described by mean, standard deviation, median, and interquartile. Statistical analysis: Appropriate methods were used for analysis according to the types of indicators. T test or Wilcoxon rank sum test was used for inter-group comparison of quantitative data, and chi-square test was used for classified data.

十四、 Testing-related Ethics

1. compliance with the requirements of the declaration of helsinki and laws and regulations

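### The sample size rests on one fMRI comparison that the protocol does not identify, and the stated tests do not use the V0 scan as a covariate

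*Protocol*

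**What the plan says.** Section 九 (Sample size assessment), repeated in the Programme summary, defines the variable that drives the sample size: "The change in blood flow volume of cerebral regions shown by fMRI after nasal insulin inhalation was used as the research endpoint". It then gives one effect and one spread, "the difference between groups after drug intervention was 20%, and the standard deviation was 20" (per cent), with a single 0.05 and power 0.8, and arrives at 23 evaluable patients per group.

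Section 十 (Study Endpoints, Effectiveness) words the primary differently: "The main evaluation indexes were the changes of cerebral blood flow shown by fMRI after nasal insulin inhalation". MoCA is ranked as secondary, so the order between imaging and cognition is clear.

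Section 六 (Research background, item 2) explains that the method serves "to observe the response of different brain regions to insulin".

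On timing, the Programme summary (Research design) says that central insulin sensitivity in the two groups "before and after treatment was evaluated by nasal insulin inhalation combined with fMRI". Section 十一 (Research process) schedules the insulin fMRI at V0 and again at V7, week 26.

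Section 十三 (Statistical Analysis Plan) states: "T test or Wilcoxon rank sum test was used for inter-group comparison of quantitative data". All tests are two-sided, and P ≤ 0.05 "was considered statistically significant for the difference tested". No covariate and no multiplicity rule are mentioned.

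**The concern.** A difference, an SD and a 0.05 have meaning only for one defined quantity. Here two things about that quantity are open.

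- **Which measure.** One wording is regional and the other speaks of blood flow in the brain at large. They are compatible, but neither picks one region, a composite or a global value.
- **Which contrast.** The sample-size wording leans towards the insulin response at V7. The Programme summary leaves a V0-to-V7 change open. The 20% SD cannot be assigned to either.

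Two things are at stake. If the region is settled only when results are known, or several regions are tested, the single 5% error rate behind the sample size is no longer assured. And the stated tests either ignore the V0 scan (V7 alone) or subtract it in full (change score), although every patient is due to have one.

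**Working it through.** **1. The plan's own figure.** Inputs from section 九: difference 20, SD 20, 0.05, power 0.80; two-sided from section 十三. Normal formula: n = 2 × (1.960 + 0.842)² × (20/20)² = 15.7, so 16 per group; the exact t test needs 17. The stated 23 is not reproduced; at 23 per group the t-test power is 91%. That mismatch is a separate point. Below, 23 per group is taken as given.

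**2. What the text identifies.**

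| Place | Measure | Contrast |
|---|---|---|
| 九 and Programme summary (Sample size) | regional flow, region(s) not named | between groups after the intervention |
| 十, Effectiveness | cerebral flow, no region or summary named | not stated |
| Programme summary (Research design) | central insulin sensitivity | before and after treatment |

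No row fixes both a measure and a contrast.

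**3. Use of the V0 scan.** Let the response have variance σ² at both visits and correlation r between V0 and V7. The documents give no r, so a range is assumed. Per-patient variance:

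- V7 alone: σ²
- V7 minus V0: 2(1 − r)σ²
- V7 adjusted for V0 (ANCOVA): (1 − r²)σ²

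The ratio of adjusted to V7 alone is 1 − r². The ratio of adjusted to change score is (1 − r²)/(2(1 − r)) = (1 + r)/2. Neither depends on the 20% SD.

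For power, assume further that the 20% is the SD of the V7 response. The SD is then 20 for V7 alone, 20√(2(1 − r)) for the change score and 20√(1 − r²) adjusted. Noncentral t, 23 per group, difference 20, two-sided 0.05; df 44, or 43 when adjusted:

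| r | Adjusted / V7 alone | Adjusted / change | Power, V7 alone | Power, V7 − V0 | Power, adjusted |
|---|---|---|---|---|---|
| 0 | 1.00 | 0.50 | 91% | 65% | 91% |
| 0.3 | 0.91 | 0.65 | 91% | 80% | 94% |
| 0.5 | 0.75 | 0.75 | 91% | 91% | 97% |
| 0.7 | 0.51 | 0.85 | 91% | 99% | over 99% |

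**4. Error rate if more than one region were primary.** The number of regions k is not in the protocol, so this is an illustration. Independent regions, each at 0.05: 1 − 0.95² = 9.8% for k = 2 and 1 − 0.95⁵ = 22.6% for k = 5. Correlated regions come from a simulation of 100,000 null trials with 23 per arm and two-sample t tests (Monte Carlo error about 0.1 percentage point):

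| Regions | Correlation 0 | 0.5 | 0.8 |
|---|---|---|---|
| 2 | 9.8% | 9.1% | 7.7% |
| 5 | 22.6% | 18.4% | 12.9% |

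With one scalar the rate is 5%.

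**The case against.** **Several primary tests are not stated.** A reader might infer that several regions will each be tested as primary and that the 5% level is already lost. The documents do not say so. The inference rests on plurals in a translated text and on a background sentence about what the technique can show; the endpoint section does not mention regions at all. This stands: inflation is a possible consequence with an assumed k. Several regions need not sink the trial either. With a Bonferroni split over three and a standardised difference of 1, power per region at 23 per group is still about 81%.

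**The unadjusted test is valid.** A reader might also infer that the analysis is wrong without the V0 covariate. It is not: randomisation justifies a plain t or Wilcoxon test. In step 3 only the change score falls below 80% power, and only if r is under 0.3 and the 20% is the SD of the V7 response. If the 20% is the SD of the change, that test has the 91%. What remains is precision that already planned data would supply.

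**No test is tied to the primary by name.** Section 十三 names tests for quantitative data in general and allows appropriate methods by type of indicator. A t test on V7 minus V0 would use the V0 scan, though not as a covariate. This stands too.

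**A separate SAP may settle it.** Covariates are often left to an SAP, and section 十九 refers to a statistical plan. But the identity of the primary variable and the meaning of the sample-size inputs belong in the protocol, and section 十三 already states tests that leave the V0 covariate out.

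**Conclusion.** The point holds in this form: the protocol sizes the trial on one comparison at 0.05 without identifying the measure or the contrast compared, and its stated tests do not use the planned V0 scan as a covariate. It should be fixed before any outcome scans are analysed; it does not invalidate the trial.

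The gain from adjustment depends on r. At r = 0.5 the variance falls to 0.75 of either alternative; at r = 0 nothing is gained over V7 alone, but the variance is half that of the change score. These ratios assume equal variances at V0 and V7. They leave aside the lost degree of freedom and the small cost of chance imbalance at V0.

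The rise in error rate, about 8–10% for two regions and 13–23% for five, is conditional on regional tests that the text permits but does not announce. The actual figure cannot be given, because the protocol states no number of regions.

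**What to change.** Before any outcome scans are analysed, the sponsor should:

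1. Name one primary scalar: one region, one composite or one global measure, with the insulin response defined from the acquisitions already planned at V0 and V7. The visit schedule lists insulin inhalation combined with fMRI but does not describe a pre-inhalation acquisition, so the definition must be checked against what is scanned.
2. Compare that scalar between groups at V7 by ANCOVA with the V0 value as covariate, in one two-sided test at 0.05.
3. Label all other regions secondary or exploratory.
4. State that the 20% difference and 20% SD refer to that scalar and contrast, or restate the power if they do not.
5. Align the Programme summary and sections 九, 十 and 十三.

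The cost is one degree of freedom, and a result in another region can no longer be called primary. No visit is added, and no scan either if the scalar can be derived from the planned acquisitions. The source of the 20%/20% has to be checked; if it does not fit the chosen scalar and contrast, the sample size must be reworked, which is more than a wording change.

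### The stated 23 per group does not follow from its own inputs: they need 16 or 17 per group for 80% power, and 23 gives about 91%

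*Protocol*

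**What the plan says.** The calculation is in the protocol, 九、 Sample size assessment, and is repeated in the Sample size row of 一、 Programme summary. The endpoint used for sizing is the primary one: "The change in blood flow volume of cerebral regions shown by fMRI after nasal insulin inhalation was used as the research endpoint".

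The inputs are attributed to earlier literature, with no reference number: "the difference between groups after drug intervention was 20%, and the standard deviation was 20" per cent. The error rates are given as "When the accuracy was 0.05" and "the test efficiency $1-\beta$ was 0.8".

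An unnamed formula is then said to give 23 per group. A 15% loss takes this to 27 per group, 54 in total.

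十三、 Statistical Analysis Plan supplies the rest: "All statistical tests were performed using a two-sided test", with significance at P ≤ 0.05, and "T test or Wilcoxon rank sum test was used for inter-group comparison of quantitative data".

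**The concern.** Every input of a two-sample comparison of means is stated, so the required number can be recomputed. A difference of one full standard deviation is a large effect, and 23 per group is visibly more than it needs at 80% power.

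This paragraph is the protocol's only quantitative reason for randomising 54 people to 26 weeks of follow-up with two nasal-insulin fMRI sessions. If the power is misreported, the trial has about 91% power for 20 points. If the SD or the difference is misreported, the true power may be 80% or some other value. If n is the wrong figure, more people are being enrolled than the design calls for. The text does not show which of these applies.

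**Working it through.** **Inputs**
- Difference 20%, SD 20%, so the standardised effect is d = 20/20 = 1.0 (九、 Sample size assessment).
- Alpha 0.05. The protocol calls it accuracy; it is read as the significance level, in line with the P ≤ 0.05 rule in 十三. Two-sided (十三).
- Power 0.80, equal groups (九).
- Two-sample t test or Wilcoxon rank sum test (十三).

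**Attempt to reproduce 23**

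Normal formula: n per group = 2 × (1.960 + 0.842)² × (SD/difference)² = 2 × (2.8016)² × 1 = 15.70, so **16**.

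Exact t test (noncentral t): 16.71, so **17**.

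Neither gives 23. Other readings, with d = 1 and 80% power unless noted:

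| Reading | n per group |
|---|---|
| Wilcoxon, efficiency 0.955 (16.71/0.955 = 17.5) | 18 |
| Wilcoxon, worst-case efficiency 0.864 (16.71/0.864 = 19.3) | 20 |
| One-sided 0.05, t test (13.1) | 14 |
| Two-sided 0.025, t test (20.3) | 21 |
| Two-sided 0.01, t test (25.1) | 26 |
| SD multiplied by √2, t test (32.4) | 33 |
| **90% power**, two-sided 0.05, t test (22.02) | **23** |

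No reading that keeps two-sided 0.05, 80% power and the stated difference and SD reaches 23. Raising the power to 90% does.

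**Power of the stated numbers (two-sided t test, d = 1)**

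| n per group | Power |
|---|---|
| 16 | 78.1% |
| 17 | 80.7% |
| 22 | 89.97% |
| 23 | 91.2% |
| 27 | 95.0% |

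**What would make 23 correct at 80% power**

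The effect detectable with 23 per group at 80% power is d = 0.845. That is a difference of 0.845 × 20 = 16.9 points at SD 20%, or an SD of 20/0.845 = 23.7% for a 20-point difference.

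**Dropout step**

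23/0.85 = 27.06. Using 27 is acceptable (27 × 0.85 = 22.95 evaluable), so this step is not the error. It also shows that 23 is the figure before dropout, so the excess is not attrition already counted in. From the t-test requirement, 17/0.85 = 20 per group, 40 in total, and 54 − 40 = 14.

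**The case against.** The arithmetic is hard to dispute. Four points can be made on the other side.

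1. **The mismatch is conservative.** On the stated inputs the trial has more power than claimed, and no endpoint, test or error rate is affected. This stands, and it limits the harm to traceability and to a possible excess of 14 participants. A null result would in any case be read mainly from the estimate and its confidence interval.

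2. **There may be an unstated step.** The endpoint refers to cerebral regions in the plural. With alpha split over three regions the t test needs 22.4, so 23; over four regions the normal formula gives 22.3, also 23. The stated difference, SD, power and n could then all stand. But the protocol mentions no such split, so the calculation as written would still be incomplete. The point does show that 90% power is not the only route to 23.

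3. **The SD is not defined.** If 20% is the SD of a single measurement and a change is analysed, the SD of the change is 20 × √(2(1 − ρ)). A correlation ρ of about 0.30 gives 23.7% and hence 23 per group. Nothing in the protocol says this was done.

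4. **The remedy should not be fitted to n.** Choosing a power or a difference because it matches 23 does not establish what was intended. If the relevant SD were 20 × √2 = 28.3%, 23 per group would have about 65% power, and 54 might then be too few. This stands, and it is why the calculation should be recovered before the text is rewritten.

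**Conclusion.** The sample size statement is wrong as written. With a 20% difference, SD 20%, two-sided 0.05 and 80% power, the requirement is 16 per group (normal formula) or 17 (t test), against a stated 23. The gap of 6 per group is about 35% of the t-test figure (6/17) and is too large to be rounding. The stated 23 gives 91.2% power, and the 27 enrolled per group would give 95.0% with no losses.

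This assumes that 0.05 is the two-sided significance level, that 20% is the SD of the quantity compared between groups, and that the comparison is a two-sample t test. The worst-case rank-sum adjustment gives 20, which is still short of 23. That 90% power was intended is plausible, because it reproduces 23 exactly, but the document does not confirm it. On the stated inputs the trial is larger than needed, not underpowered.

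**What to change.** Recover the original calculation and correct the same text in 九、 Sample size assessment and in the Programme summary. State the difference, the SD and what it is the SD of (a single measurement or a change), the two-sided alpha and any division of it across regions, the power, the test and n, and check that they agree. Cite the source of the 20% difference and the SD.

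If the stated difference and SD are confirmed and 54 is kept, say what 54 delivers. With 23 evaluable per group and SD 20%, that is 91% power for a 20-point difference or, equivalently, 80% power for a 16.9-point difference. If the intended SD was about 24%, state that SD and keep 80%.

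On any of these routes the cost is protocol wording, with no change in enrolment. Enrolment would need another look only if the recovered inputs no longer support 54, for example if the SD proves clearly above 24%.
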